11.4 Analysis of Secondary Endpoints

The Phase II Portion will include estimating overall survival, progression-free survival, and toxicity rates. Assuming 33 eligible patients are enrolled, this will be sufficient to estimate overall survival, progression-free survival, and toxicity rates to within \pm 17% (95% confidence interval). Assuming 33 eligible patients overall, any toxicity with at least a 5% chance of occurring has a 82% chance of being observed at least once. In addition, to assess safety and feasibility in both the Phase I and Phase II Portions of the trial, descriptive statistics will be presented for the number of patients requiring dose reduction, interruption or discontinuation and the percentage of dose delivery.

11.5 Analysis of Translational Medicine Component

This analysis will include those patients enrolled to the Phase I or II Portion of the study with adequate specimens. Every attempt will be made for pre-study collection of blood and tissue specimens. Blood and tissue specimens from accessible metastatic lesions will be requested from two other time points: 1) after start on therapy (approximately Day 15-30), and 2) at the time of progression on this study.

For the pre-study time point, for each of the categorical markers listed in Section 18.2, we will estimate the prevalence of the marker in this patient population. For binary markers, the prevalence will be able to be estimated and exact binomial confidence interval will be calculated. The association between these categorical markers and clinical outcomes will be explored in a preliminary manner, using Fisher's exact test to compare response and a logrank test to compare Kaplan-Meier estimates of OS and PFS between marker positive and marker negative groups.

For the quantitative markers in the previous section, we will estimate median and range values in this patient population. The association between quantitative markers and clinical outcomes will be explored in a preliminary manner, using the Wilcoxon-rank sum

test to assess response and Cox regression to assess PFS and OS. In addition, we may explore dichotomizing the patients into two groups by splitting at the median (or other cutpoints may be explored) and applying the methods specified above for the categorical markers.

For patients with samples at more than one time we will examine changes in marker status over time. This analysis will be very exploratory.

For patients enrolled on the Phase I Portion, PK sampling steady state should be taken at baseline, pre-dose Day 15 and pre-dose Day 29. In addition, three patients treated within the second cohort of each of the Phase I Portions (D+G and D+T+G) will have more extensive PK sampling at baseline, pre-dose and +1, +2, +4, and +8 hours on Day 15, and pre-dose Day 29.

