1.4 Translational Medicine Objective

- a. The translational medicine objective is to explore the molecular mechanisms of acquired resistance to BRAF inhibitor therapy using available biopsies of lesions that progressed during prior BRAF inhibitor-based therapy. The analyses will include the following to detect MAPK-reactivation resistance: Detection of BRAF^{V600} amplification, BRAF^{V600} truncation, NRAS^{Q61} mutations and MEK mutations, which are the most validated and readily detectable acquired MAPK-reactivation resistance mechanisms. Additional analyses to detect other mechanisms of resistance, particularly those involving the AKT pathway, will be explored, as will be targeted sequencing of genes in the P13K/AKT pathway.
- b. All patients participating in the Phase I portions of the study will have a limited PK sampling at baseline and at steady state on Days 15 and 29 before taking the study drugs on that day. In addition, three patients treated within the second cohort of each of the Phase I portions (D+G and D+T+G) will undergo an intense 15 day pharmacokinetic (PK) sampling for circulating levels of the study drugs. This will be performed to explore potential drug-drug interactions between dabrafenib and GSK2141795 leading to changes in the expected exposure with either agent compared to prior experience.

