5.0 ELIGIBILITY CRITERIA

Each of the criteria in the following section must be met in order for a patient to be considered eligible for registration. Use the spaces provided to confirm a patient's eligibility. For each criterion requiring test results and dates, please record this information on the Onstudy Form and submit via Medidata Rave® (see Section 14.0). Any potential eligibility issues should be addressed to the Data Operations Center in Seattle at [name] prior to registration.

In calculating days of tests and measurements, the day a test or measurement is done is considered Day 0. Therefore, if a test is done on a Monday, the Monday 2 weeks later would be considered Day 14. This allows for efficient patient scheduling without exceeding the guidelines. If Day 14, 28 or 42 falls on a weekend or holiday, the limit may be extended to the next working day.

SWOG Patient No Patient's Initials (L, F, M)			
		a.	Patients must have $BRAF^{V600}$ mutant metastatic cancer irrespective of the histology or prior therapy. $BRAF^{V600}$ mutant status must be documented by a CLIA-certified laboratory. Use of an FDA-approved test is preferred although other BRAF tests at a CLIA-certified laboratory may also be accepted.
		b.	Patients must have locally advanced unresectable Stage IIIC or metastatic Stage IV cancer with either progression to prior therapy or a newly diagnosed cancer that does not have an available treatment with curative intent. See Section 4.0 for staging criteria.
		C.	Patients must have a complete physical examination and medical history within 28 days prior to registration.
		d.	Patients must have measurable or non-measurable disease as defined in Section 10.1 . All measurable lesions must be assessed (by physical examination, CT, or MRI scan) within 28 days prior to registration. Tests to assess non-measurable disease must be performed within 42 days prior to registration. All disease must be assessed and documented on the Baseline Tumor Assessment Form (RECIST 1.1).
		e.	All patients must undergo a CT or MRI of the brain within 42 days prior to registration. Patients with asymptomatic brain metastases or previously treated brain metastases that are stable (i.e. not requiring corticosteroids) at the time of registration will be eligible.

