		f.	Patients may have received prior systemic therapy (chemotherapy, immunotherapy, biologic therapy, or combination regimens). All adverse events associated with prior treatment must have resolved to \leq Grade 1 prior to registration.

swog	Patient	No	
Patient'	's Initia	ls (L, F,	M)
		g.	Patients progressing on a prior BRAF inhibitor-based therapy will be eligible, as are patients naïve to BRAF inhibitor therapy. Resistance to BRAF inhibitor-based therapy will be defined as progressive disease by RECIST 1.1 criteria while receiving therapy with a BRAF inhibitor (vemurafenib or dabrafenib, alone or in combination with a MEK inhibitor). This may be innate resistance (patients who never achieved a tumor response while on BRAF inhibitor therapy) or acquired resistance (progression after having a tumor response to BRAF inhibitor therapy). There will not be a period of break between progression on the prior BRAF inhibitor-based therapy and the start of dabrafenib, trametinib and GSK2141795.
		h.	Patients may have received prior surgery (for both the primary and Stage IV disease). All adverse events associated with prior surgery must have resolved to ≤ Grade 1 prior to registration.
		i.	Patients may have received prior radiation therapy. All adverse events associated with prior radiation therapy must have resolved to \leq Grade 1 prior to registration.
		- j.	Patients must be willing to submit blood for pharmacokinetics (see Section 15.3). Sites must order S1221 PK kit immediately after registration (see Section 18.6). The SWOG patient ID number must be provided on the S1221 PK Kit Request Form.
		k.	Patients must have available and be willing to submit baseline tissue taken at the time of disease progression to prior BRAF inhibitor-based therapy (either fresh frozen [preferred], or paraffin-embedded tumor blocks) OR must have a site of disease that can be biopsied within this study for translational medicine studies outlined in Section 15.4 and Section 18.2 . Tissue may be from an archival biopsy or a new biopsy after the patient has been registered to the protocol. Since patients are referred to this protocol after progression on prior BRAF inhibitor-based therapy, the biopsy taken at the time of progression will be used as the baseline biopsy for this study. Patients must be willing to submit plasma and whole blood for translational medicine studies as outlined in Section 15.4 and Section 18.2 .

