6.0 STRATIFICATION FACTORS

This section is not applicable.

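### Section 11.5 does not limit the resistance-marker analyses to patients who progressed on a BRAF inhibitor, as Sections 1.4a and 18.2 do, and its tests are not stratified by prior exposure

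*Combined protocol and SAP*

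**What the plan says.** Section 11.5 sets the population: "This analysis will include those patients enrolled to the Phase I or II Portion of the study with adequate specimens". For the pre-study time point it estimates the prevalence of each categorical marker listed in Section 18.2, with exact binomial intervals for binary markers. It then relates markers to outcome "using Fisher's exact test to compare response and a logrank test to compare Kaplan-Meier estimates of OS and PFS" between marker groups. Quantitative markers get Wilcoxon rank-sum tests and Cox regression. No stratum or covariate is named, and Section 6.0 on stratification factors reads "This section is not applicable". The associations "will be explored in a preliminary manner". Section 11.5 states no significance level.

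Phase I is broad. Section 5.1a takes "metastatic cancer irrespective of the histology or prior therapy". Section 5.1g says "Patients progressing on a prior BRAF inhibitor-based therapy will be eligible" and, in the same sentence, admits patients naive to BRAF inhibitors. Section 5.1k requires either tissue taken at progression on prior BRAF inhibitor therapy or a site of disease that can be biopsied on study. Phase II requires melanoma and recent prior BRAF inhibitor therapy (Sections 5.2a and 5.2b), so it contributes no naive patients.

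Two other passages are narrower. Objective 1.4a studies acquired resistance "using available biopsies of lesions that progressed during prior BRAF inhibitor-based therapy". Section 18.2 describes the pre-study specimen as one obtained after failure of first-line BRAF inhibitor therapy.

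**The concern.** The objective is about mechanisms of acquired resistance, a question about tumours that have escaped a BRAF inhibitor. The population sentence in 11.5 carries no such condition, and a naive Phase I patient with an adequate biopsy satisfies it.

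Two consequences follow if naive patients enter:

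- **Prevalence.** Naive tumours are not expected to carry acquired changes often, so a pooled proportion, with its exact interval, describes a mixture of two populations and falls below the figure for resistant tumours.
- **Association.** Prior exposure bears on both variables. Exposed patients are more likely to carry the marker and less likely to respond. A marker with no effect in either group can then look like a predictor of non-response. Calling the analysis preliminary allows for imprecision and multiple testing, but does not remove a bias whose direction is known in advance.

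**Working it through.** **1. The plan's own figure.** Section 11.1 gives up to 12 (D+G Phase I), 18 (D+T+G Phase I) and 33 (Phase II) patients, with 10% ineligible or not evaluable: (12 + 18 + 33) / 0.90 = 63 / 0.90 = 70. This matches the stated total of approximately 70. At full accrual, up to 30 of the 63 come from Phase I, where naive patients are allowed. The documents do not say how many will be naive.

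**2. Inputs.**

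| Input | Value | Source |
|---|---|---|
| Resistant / naive patients | 45 / 10 | assumed |
| Marker prevalence, resistant | 22% (PI3K-pathway mutations) or 70% (all MAPK reactivation, among cases with a known or proposed mechanism) | Section 2.0 |
| Marker prevalence, resistant, intermediate | 30% | assumed |
| Marker prevalence, naive | 5% | assumed |
| Response, resistant | 15% (upper end of 9-15% on dabrafenib + trametinib after a BRAF inhibitor) | Section 2.0 |
| Response, naive | 76% (150/2 arm) or 54% (dabrafenib alone) | table in Section 2.0 |
| Marker effect within each group | none | null scenario |
| Test level | two-sided 0.05 | assumed |

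**3. Dilution.** Pooled prevalence = (45 × p_R + 10 × 0.05) / 55, where p_R is the prevalence in resistant patients.

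- 70% marker: (31.5 + 0.5) / 55 = 58%
- 30% marker: (13.5 + 0.5) / 55 = 25%
- 22% marker: (9.9 + 0.5) / 55 = 19%

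**4. Spurious difference in response.** With no marker effect, the expected response in each pooled marker group is a weighted average of the two patient groups. For the 70% marker and 76% naive response:

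- marker-positive: (31.5 × 0.15 + 0.5 × 0.76) / 32 = 5.105 / 32 = 16%
- marker-negative: (13.5 × 0.15 + 9.5 × 0.76) / 23 = 9.245 / 23 = 40%

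For the 22% marker and 76% naive response:

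- marker-positive: (9.9 × 0.15 + 0.5 × 0.76) / 10.4 = 1.865 / 10.4 = 18%
- marker-negative: (35.1 × 0.15 + 9.5 × 0.76) / 44.6 = 12.485 / 44.6 = 28%

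**5. How often Fisher's test rejects.** Simulation with marker and response independent within each group:

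| Marker prevalence (resistant) | Naive response | Pooled test | Resistant only |
|---|---|---|---|
| 22% | 76% | about 5% | 2-3% |
| 30% | 76% | about 9% | 2-3% |
| 70% | 54% | about 23% | 2-3% |
| 70% | 76% | about 47% | 2-3% |

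With 5 naive patients instead of 10, the last row falls to 18-20%.

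**6. Sensitivity to the naive share, and effect of stratifying.** A second simulation used 63 patients, zero marker prevalence in naive patients, and response of 76% (naive) and 15% (resistant). The pooled test rejected as follows:

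| Naive of 63 | 70% marker | 22% marker |
|---|---|---|
| 15 | 77% | 11% |
| 8 | 40% | 3% |
| 4 | 14% | 2% |

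An exact test stratified by prior BRAF inhibitor exposure rejected in 2-3% of trials in these cases, and in 1.2-3.8% across all scenarios run.

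**The case against.** The strongest reply is that the restriction already exists. Section 11.5 analyses the pre-study time point for markers listed in 18.2, and 18.2 describes that specimen as post-failure. Section 5.1k also says that the progression biopsy will serve as baseline, and 1.4a agrees. Read together, an adequate specimen could mean a post-progression one. This stands to a degree: a reader might infer that the plan has chosen to pool naive and resistant patients, and the documents do not support that. They do not settle the opposite either. The cross-reference in 11.5 is to the marker list, its only stated condition on specimens is adequacy, and 5.1k offers the on-study biopsy as an alternative. The passages are inconsistent.

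The second reply concerns size, and most of it stands. The 70% figure is a composite of mechanisms, whereas 18.2 lists markers individually. No listed marker is given a 70% prevalence. The 76% response comes from melanoma patients on dabrafenib 150 mg with trametinib 2 mg, while naive Phase I patients may have other histologies or receive no trametinib. The 47% is therefore the upper end of the 45 + 10 scenarios, not an expected error rate, and it is measured against a level that the plan does not set.

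A reader might also infer that pooling two regimens and several histologies confounds the tests. That is not shown. Either would confound a pre-treatment marker only if marker prevalence differed across regimens or histologies as well as response, and the documents give no evidence of this. They also disagree on histology: the treatment-arm table in Section 2.0 lists D+T+G Phase I as melanoma, while 5.1a accepts any histology.

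**Conclusion.** The point holds as an inconsistency with a conditional bias. Sections 11.5, 5.1g and 5.1k allow naive patients into the marker analyses; 1.4a and 18.2 describe post-progression specimens. If 11.5 is followed literally and naive patients supply tissue, prevalence is diluted (70% reads as 58%, and 22% as 19%, with 45 resistant and 10 naive patients). The false-positive rate of the pooled Fisher test then runs from about 5%, which is no inflation over the assumed level, to about 47%, against 2-3% in resistant patients alone.

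The size depends on the naive share, the marker prevalence and the naive response rate, none of which the documents fix for this population. The 5% prevalence in naive patients and the two-sided 0.05 level are assumptions. With no naive patients there is no bias from this source. The analysis is exploratory, no decision rests on it, and the primary endpoint is unaffected because Section 11.3b keeps Phase I patients out of the Phase II analysis.

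**What to change.** State in Section 11.5 that prevalence estimates and the main marker-outcome analyses use baseline specimens taken at or after progression on BRAF inhibitor-based therapy, in line with 1.4a and 18.2. If naive patients are also analysed, report their prevalence separately and stratify the association tests by prior BRAF inhibitor exposure: an exact stratified test for response, and stratified logrank and Cox analyses for PFS and OS. Results may be described by regimen and histology, without formal adjustment.

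The cost is a few sentences of text, with no new data or patients. The downside is slightly fewer patients in the main marker analysis.

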11.6 Data and Safety Monitoring

See Section 15.0, description of conference calls for safety monitoring of the Phase I Portion and selection of the recommended Phase II dose.

There is no formal data and safety monitoring committee for single arm Phase II studies. Toxicity and accrual monitoring are done routinely by the Study Chair, study Statistician and the Disease Committee Chair. Endpoint monitoring is done by the study Statistician and Study Chair. Accrual reports are generated weekly, and formal toxicity reports are generated every 6 months. In addition, the Statistical Center, Adverse Event Chair at the Operations Office, SAE Physician Reviewer, and Study Chair monitor toxicities on an ongoing basis.

12.0 DISCIPLINE REVIEW

This study will not utilize discipline review.

13.0 REGISTRATION GUIDELINES

13.1 Registration Timing

Patients must be registered prior to initiation of treatment (no more than eight working days prior to planned start of treatment). If enrolling a patient onto the Phase I portion, sites must order S1221 PK kit immediately after registration (see Section 18.6). The SWOG patient ID number must be provided on the S1221 PK Kit Request Form. Allow up to five working days for the PK kit to arrive.

13.2 Slot Reservation

Patients planning to enroll on this study must first have a slot reserved in advance of the registration, even if the site plans to enroll right away. All site staff will use OPEN to create a slot reservation. OPEN is a web-based application and can be accessed at https://open.ctsu.org, or from the OPEN tab on the CTSU members' side of the website at https://www.ctsu.org, or from the OPEN Patient Registration link on the SWOG CRA Workbench. Please refer to the 'Slot Reservation Quick Reference Site User Guide' within the OPEN tab on the CTSU members' website under 'Training and Demonstration Materials' for detailed instructions.

The individual making the slot reservation for the patient must be prepared to provide answers to the following questions:

- Institution CTEP ID
- b. Protocol Number
- c. Registration Step
- d. Patient Initials
- e. Patient's Date of Birth
- f. ZIP Code
- g. Gender (select one):
 - Female Gender
 - Male Gender

Slot reservations expire within 28 calendar days. A warning e-mail will be sent 48 hours before the expiration date. The reservation can be renewed any time before it expires as long as at least 1 slot is still available. After it expires, a new slot reservation must be created for the patient before they can be enrolled to this trial. Reservations may also be withdrawn at any time. If you withdraw a reservation, please notify the Statistical Center at [contact].

13.3 OPEN Registration Requirements

The individual registering the patient must have completed the appropriate SWOG Registration Worksheet. The completed form must be referred to during the registration but should not be submitted as part of the patient data.

OPEN will also ask additional questions that are not present on the SWOG Registration Worksheet. The individual registering the patient must be prepared to provide answers to the following questions:

- a. Institution CTEP ID
- b. Protocol Number
- c. Registration Step
- d. Treating Investigator
- e. Credit Investigator
- f. Patient Initials
- g. Patient's Date of Birth
- h. Patient SSN (SSN is desired, but optional. Do not enter invalid numbers.)
- i. Country of Residence
- j. ZIP Code
- k. Gender (select one):
 - Female Gender
 - Male Gender

- I. Ethnicity (select one):
 - Hispanic or Latino
 - Not Hispanic or Latino
 - Unknown
- m. Method of Payment (select one):
 - Private Insurance
 - Medicare
 - Medicare and Private Insurance
 - Medicaid
 - Medicaid and Medicare
 - Military or Veterans Sponsored NOS
 - Military Sponsored (Including Champus & Tricare)
 - Veterans Sponsored
 - Self Pay (No Insurance)
 - No Means of Payment (No Insurance)
 - Other
 - Unknown
- n. Race (select all that apply):
 - American Indian or Alaska Native
 - Asian
 - Black or African American
 - Native Hawaiian or other Pacific Islander
 - White
 - Unknown

13.4 Registration Procedures

- a. All site staff will use OPEN to enroll patients to this study. OPEN is a web-based application and can be accessed at https://open.ctsu.org, or from the OPEN tab on the CTSU members' side of the website at https://www.ctsu.org, or from the OPEN Patient Registration link on the SWOG CRA Workbench.
- b. Prior to accessing OPEN site staff should verify the following:
 - All eligibility criteria have been met within the protocol stated timeframes and the affirmation of eligibility on the Registration Worksheet has been signed by the registering investigator or another investigator designate. Site staff should refer to Section 5.0 to verify eligibility.
 - All patients have signed an appropriate consent form and HIPAA authorization form (if applicable).
- c. Access requirements for OPEN:
 - Site staff will need to be registered with CTEP and have a valid and active CTEP-IAM account. This is the same account (user ID and password) used for the CTSU members' web site.
 - To perform registrations on SWOG protocols you must have an equivalent 'Registrar' role on the SWOG roster. Role assignments are handled through SWOG.

Note: The OPEN system will provide the site with a printable confirmation of registration and treatment information. Please print this confirmation for your records.

- d. Further instructional information is provided on the OPEN tab on the CTSU members' side of the website at https://www.ctsu.org or at https://open.ctsu.org. For any additional questions contact the CTSU Help Desk at [name] or [contact].
- 13.5 Exceptions to SWOG registration policies will not be permitted.
 - a. Patients must meet all eligibility requirements.
 - b. Institutions must be identified as approved for registration.
 - c. Registrations may not be cancelled.
 - d. Late registrations (after initiation of treatment) will not be accepted.

